10.6 Electrocardiogram

A 12-lead electrocardiogram (ECG) will be performed at baseline. Clinically relevant abnormalities found will be reported on the medical history page. The investigator may perform additional unscheduled examinations to manage or evaluate a suspected SAE as clinically necessary. The data of all subsequent ECGs will be reported on the ECG/Echocardiogram CRF.

10.7 Echocardiogram

The last echocardiogram done prior to admission will be collected as well as any echocardiogram performed during admission. Clinically relevant abnormalities found will be reported on the medical history page. The data of all subsequent Echocardiograms will be reported on the ECG/Echocardiogram CRF.

10.8 Child-Pugh Scores

Child-Pugh score will be calculated at baseline and entered in the CRF.

11 Detail of Safety Assessments and Procedures

11.1 Vital Signs

Vital sign measurements will be recorded at baseline and daily during study drug administration. The measurements should be assessed and recorded at a consistent, specific time of day, preferable morning assessment/measurement.

Systolic and diastolic blood pressure, heart rate, body temperature, respiratory rate, and pulse oximetric saturation (SpO₂) will be recorded at baseline and during study drug administration.

11.2 Encephalopathy Score

Clinically detectable encephalopathy is to be assessed prior to study drug administration and daily during study drug administration using the clinical criteria described in Table 3.

Table 3 **West Haven Criteria for Semiquantitative Grading of Mental State**

Grade 1	Trivial lack of awareness. Euphoria or anxiety. Shortened attention span. Impaired performance of addition.
Grade 2	Lethargy or apathy. Minimal disorientation for time or place. Subtle personality change. Inappropriate behavior. Impaired performance of subtraction.
Grade 3	Somnolence to semi-stupor, but responsive to verbal stimuli. Confusion. Gross disorientation.
Grade 4	Coma (unresponsive to verbal or noxious stimuli).

Source: Ferenci et al, 2002.

11.3 Model for End-Stage Liver Disease Score

Model for end-stage liver disease (MELD) scores will be calculated by the sponsor based on SCr, bilirubin and INR values at baseline and treatment termination.

11.4 Adverse Events

Only Serious Adverse Events will be recorded until 30 days after discontinuation of study drug.

Those events that are unanticipated serious adverse events possibly related to the study drug (SUSAR) must be reported to the sponsor or its designee for safety reporting in an expedited. See section 14.2 for SUSAR definition.

12 Detail of Laboratory Assessments and Procedures

12.1 Local Laboratory at Investigational Site

The laboratory tests specified in this section will be performed in the laboratory at the investigational site. All efforts should be made to take the blood sample from a clean new venous site, or the second option could be a central venous line to collect the blood specimen. Site

personnel should not draw the blood sample from an existing peripheral venous access site, or a line used for IV fluid administration.

12.2 Serum Electrolytes & Biochemistry

The following assessments are required at baseline, then once daily during treatment or hospital discharge (whichever occurs first):

- Creatinine level (SCr)
- Blood urea nitrogen (BUN, if taken as per standard of care)
- Estimated Glomerular Filtration Rate (eGFR, if taken as per standard of care)

If SCr, BUN and/or eGFR assessments are performed more than once daily as part of the subject's medical care, all values are to be recorded on the CRF.

SCr (BUN & eGFR if also taken standard of care) are to be collected and recorded at all Follow-up Visits including: Day 7, 14, 30, 90, 180 and 365 as per standard of care.

The following assessments are required at baseline and daily during treatment with study drug:

- Sodium
- Potassium
- Chloride
- HCO_3
- 24 Hour Urine Output (if available)

The following assessments are required at baseline and on treatment days 1, 3, 7, and, whenever possible, at treatment termination:

- Total bilirubin*
- Alkaline phosphatase (ALP)*
- Alanine aminotransferase (ALT)*
- Aspartate aminotransferase (AST)*
- Total protein*
- Albumin*
- Glucose

*Total Bilirubin, ALP, ALT, AST, Total Protein, and Albumin are to be collected and recorded at all Follow-up Visits including: Day 7, 14, 30, 90, 180 and 365 if taken as per standard of care.

The following assessments are optional:

- Collection of blood & urine for future biomarker evaluation - optional at baseline (pretreatment), on treatment day 4, and at treatment termination
- Cystatin C - optional at baseline (pretreatment), treatment day 4, and at treatment termination

12.3 Hematology

The following assessments are required at baseline and on treatment days 1, 3, 7, and, whenever possible, at treatment termination:

- International normalized ratio (INR)
- Complete blood count (CBC) (no differential required, but neutrophils and lymphocytes if available)

INR is to be collected and recorded at all Follow-up Visits including: Day 7, 14, 30, 90, 180 and 365 as per standard of care.

12.4 Total Volume of Blood Collected

The total volume of blood collected from each subject over the course of 14 days and end of study should not exceed approximately 310 mL, and is standard of care for the subject being treated. All blood draws and assessments requested are to follow standard of care procedures.

13 Detail of Efficacy Assessments and Procedures

Serum creatinine must be collected at enrollment (prior to study dosing), and at least once daily during treatment until Day 14 or hospital discharge, whichever occurs first. If SCr assessments are performed more than once daily as part of the subject's medical care, all values obtained each day will be recorded on the CRF.

13.1 Primary Efficacy Variable

Improvement of renal function (SCr) from Day 1 through end of treatment, repeated measure analysis. SCr will be collected at baseline and daily from Day 1 through end of treatment.

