- If 72 hours after final dose escalation, there is no further improvement in SCr, continuation of terlipressin is at the discretion of the Principal Investigator at the clinical site.
- If a subject is initiated on RRT, terlipressin can be continued for a maximum of 72 hours after initiation of RRT.
- Terlipressin must be discontinued when the subject is to undergo liver transplantation, TIPS, or any other vasopressor therapy (single administration of vasopressor for cardiac stress test is acceptable)
- Dosing must be permanently discontinued if an event of cardiac ischemia or mesenteric ischemia occurs.

Retreatment:

If judged by the investigator to be potentially beneficial, subjects who demonstrate at least a partial response during the initial treatment course (at least 50% reduction in SCr) and develop recurrence of HRS-AKI may be retreated for a maximum of 14 days. To qualify for retreatment the subject must again meet the study inclusion/exclusion criteria. Retreatment may occur within 90 days of the subject's first dose of terlipressin.

Duration of Treatment:

For the Prospective Terlipressin Group, the active treatment period will be up to 14 days, allowing 1 retreatment cycle.

For both Prospective and Retrospective Subjects:

All subjects will be followed:

Post treatment clinical data collection will be through phone call and chart review. Creatinine, BUN and eGFR will be recorded per standard of care, recording mortality and the date of last dialysis (CVVH or HD) session for the following time points:

Collaborative Research Study, Version 4: 06/29/21
To Treat HRS-AKI Patients with Continuous Terlipressin Infusion

Day 7 +/- 2 days;
Day 14 +/- 3 days;
Day 30 +/- 1 week and
Day 90 +/- 1 week
Day 180 +/- 2 weeks and
Day 365 +/- 2 weeks.

For subjects who have a liver transplant Post Treatment

If the subject has a liver transplant recorded prior to the 90-Day visit (phone call or chart review), additional follow up will occur through one year after liver transplant.

Creatinine, BUN and eGFR will be recorded per standard of care, recording mortality and the date of last dialysis (CVVH or HD) session for the following time points:

Day 0 (date of transplant) – record allocation MELD and last calculated MELD prior to transplant;
Day 7 +/- 2 days;
Day 14 +/- 3 days;
Day 30 +/- 1 week,
Day 90 +/- 1 week,
Day 180 +/- 2 weeks and
Day 365 +/- 2 weeks.

Key Efficacy and Safety Data Assessment:

Primary Efficacy Assessment:

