8.4 Administration

Subjects in the Prospective Terlipressin Group:

Single-use, sterile 6-mL vials containing 1 mg of lyophilized terlipressin acetate (equivalent to 0.85 mg terlipressin free base) with 10 mg mannitol as a bulking agent/stabilizer.

- For initial bolus dose of 0.5mg, the vial will be reconstituted with 5 mL of sterile 0.9% sodium chloride solution and given over 1-minute push.
- Continued dosing will be by 2mg infusion per day for Days 1, and 2. For continuous infusion, the dose of terlipressin is to be dissolved in 0.9% sodium chloride solution and infused with a pump.
- If on Day 3 the SCr is not 30% lower from the baseline value, increase infusion dose to 4 mg per day.
- If on Day 5 the SCr is not 50% lower from the baseline value, increase infusion dose to 6-8 mg per day, per PI discretion. Dosing can be increased by more than 1 mg increment at Day 5 or beyond, up to a maximum of 8 mg/day.
- If the subject has infusion stopped for \geq 4 hours, a 0.5 mg bolus should be given prior to restarting infusion.
- The drug should not be used in subjects with severe coronary artery disease or in the setting of circulatory overload, pulmonary edema, or bronchospasm as determined by the Investigator. If drug therapy has been initiated, Investigator can also decide not to increase the dose, based on the patient's status with regard to the above, based on individual subject condition.

- If dosing is interrupted due to an adverse event, terlipressin may be re-started, at the discretion of the investigator, at the same or lower dose as per protocol. Terlipressin will not be restarted if dosing was interrupted due to cardiac ischemia or mesenteric ischemia.

Subjects in the Retrospective Control Group:

The dose and method of administration for Midodrine/Octreotide (M&O), albumin, or other vasopressor will be recorded as noted in the patient's medical record. To be included as a completed subject in this study, patients must have been treated for at least 48 hours with albumin infusions beyond volume resuscitation and diuretic withdrawal. Vasopressors also need to be used for a minimum of 48 hours.

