Record RRT, TIPS, transplant, and mortality ^j			Monitor and record throughout active study period and follow-up.																		
Record all paracentesis events			Record all paracentesis performed until drug treatment discontinued																		

Collaborative Research Study, Version 4: 06/29/21
To Treat HRS-AKI Patients with Continuous Terlipressin Infusion

All assessments are completed per Standard of Care.

^aMaximum treatment of 14 Days.

^bFemale subjects of child-bearing potential must have a negative urine or serum pregnancy test within 14 days prior to the first dose of study treatment.

^cThe qualifying SCr value (SCr value at least 48 hours after both diuretic withdrawal and the beginning of albumin fluid challenge) is considered the Enrollment SCr and must be drawn prior to start of study drug. The qualifying SCr value must be ≥ 1.5 mg/dL AND Baseline SCr is defined as the most recent, lowest SCr within last 6 months before date of current admission.

^dA general standard of care physical assessment of the major body systems evaluating any new clinically significant abnormalities within the following: general appearance, skin, head/eyes/ears/nose/throat, neck, heart, lungs, abdomen, extremities, and neurological systems. The investigator may perform additional unscheduled examinations to manage or evaluate a suspected AE as clinically necessary. The physical examination will also include weight and height.

^eCollection of the data from the last electrocardiogram done prior to admission and the electrocardiogram performed during admission, if performed as per standard of care

^fMust be performed at least once daily during active treatment AND until Day 14 (regardless of treatment status) or discharge, whichever occurs first. BUN & eGFR are recorded if taken per site standard of care. If assessments are performed more than once daily as part of the subject's medical care, all values are to be recorded on the CRF. If subject has SCr, BUN and/or eGFR, including Vital signs taken at any of the Follow-up Periods, they are to be recorded on the CRF.

^gSerious Adverse Events will be required to be collected only for the Prospective Terlipressin Group.

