13.2 Secondary Efficacy Variables

- Improvement of renal function (SCr) from Day 1 through end of treatment, repeated measure analysis as compared to the Retrospective Control Group.
- For the Prospective Terlipressin Group alone and also in comparison to the Retrospective Control Group:
 - Incidence of dialysis by Day 30 and Day 90 of follow up.
 - Survival by Day 30 and Day 90 follow up.
 - Transplant by Day 30 and Day 90 follow up.
 - Serum creatinine at Day 30 and Day 90 follow up
 - Serum creatinine and incidence of dialysis at Day 30, Day 90, Day 180, and Day 365 after liver transplantation
 - Incidence of kidney transplant within one year after liver transplant
 - Descriptive analysis of number simultaneous liver kidney transplants and episodes of graft rejection at Day 90 and Day 365 after liver transplant

14 Serious Adverse Events

Only Serious Adverse Events will be collected for this study for the prospective group only. Safety review and assessments will be made only for the Prospective Terlipressin Group from time of first dose through 30 days after end of treatment. SAEs are collected from the start of study drug until 30 days after study drug was discontinued. Non-serious Adverse Events are not required to be collected for this study.

The investigator will record the nature, causality, severity, treatment, and outcome of the SAE, and will determine whether there is a “reasonable probability” that the study drug treatment caused the event.

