15.1 Primary Analysis

The primary analysis will utilize mixed effects regression modeling to estimate changes in serum creatinine (SCr) over the study period, accounting for baseline SCr and the correlation structure between the repeated measures. All potential confounders will be added to the model and sequentially removed if they do not confound the association between receipt of terlipressin and improvement in Scr. Those confounders resulting in a $\geq 10\%$ change in the coefficient for the association between terlipressin and improvement in SCr will be retained in the final model. For all generated models, Aikaike Information Criteria (AIC) scores will be calculated and compared. The model with the smallest absolute AIC value will be accepted as the most parsimonious and will be used as the primary model for the explanation of study results. As has been undertaken in other terlipressin studies in HRS, a least-squares means analysis will be conducted using a repeated-measures analysis of variance. The results from this approach to the statistical analysis can then be directly compared to prior study results.

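### No rule says how creatinine drawn after dialysis starts is analysed, so dialysis-lowered values may enter the primary SCr model by default

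*Combined protocol and SAP*

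**What the plan says.** - **Primary variable (13.1; same window in the synopsis and 5.1).** "Improvement of renal function (SCr) from Day 1 through end of treatment, repeated measure analysis".
- **Primary model (15.1).** The plan uses "mixed effects regression modeling to estimate changes in serum creatinine (SCr) over the study period", accounting for baseline SCr and within-subject correlation, with confounders chosen by their effect on the terlipressin coefficient. The study period is not defined.
- **Comparison with controls (13.2).** The same variable is a secondary endpoint: "repeated measure analysis as compared to the Retrospective Control Group". For controls the plan sets minimum treatment times, for example "Vasopressors also need to be used for a minimum of 48 hours" (8.4), but no Day 1 and no end of treatment.
- **RRT during treatment (synopsis, Treatment Discontinuation).** "If a subject is initiated on RRT, terlipressin can be continued for a maximum of 72 hours after initiation of RRT".
- **SCr collection.** SCr is drawn at least daily. If it is measured more often, "all values are to be recorded on the CRF" (Table 1, footnote f); the opening of section 13 repeats that "all values obtained each day will be recorded on the CRF".
- **RRT record.** Table 1 has a row "Record RRT, TIPS, transplant, and mortality", covering treatment and follow-up. The follow-up text in the synopsis names the date of the last dialysis session, not the first.

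**The concern.** Dialysis clears creatinine. A value drawn after RRT has begun reflects the machine as well as the kidney, and RRT is itself a sign that the kidney has not recovered. The 72-hour allowance places such values inside even the narrower 13.1 window. Sections 13, 13.1, 13.2, 15.1 and 15.2 and the Table 1 footnotes do not exclude, censor, re-score or count them as failure. Adjusting for baseline SCr, correlation and confounders does not separate dialysis clearance from drug response. At stake is whether the primary SCr estimate measures renal improvement, or a mixture in which some of the sickest subjects look better because they were dialysed.

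**Working it through.** **The plan's own figures.** The plan gives no figure on this point. Its only calculation for the SCr endpoint is the detectable-difference table in 15.3: (1.960 + 0.842) × sqrt(1/50 + 1/150) × SD = 0.4575 × SD. That gives 0.46 at SD 1.00 and 0.23 at SD 0.50, as stated. Below I use those two SDs only as a scale.

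**Inputs.**
- From the documents: 50 terlipressin subjects; treatment up to 14 days; at most 72 hours on drug after RRT starts, which at one value a day is 72/24 = 3 values.
- Assumed, because the documents do not give them: share dialysed during treatment r = 10-30% (central 20%); fall in each affected value d = 1.0-2.0 mg/dL (central 1.5); affected values k = 1 to 3; a shorter course of m = 8 days beside the 14-day maximum.

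**Shift in the terlipressin-group mean, averaged over all m days** = r × d × k/m.

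| r, d | k | m = 8 | m = 14 |
|---|---|---|---|
| 0.20, 1.5 | 1 | 0.30 × 1/8 = 0.04 | 0.30 × 1/14 = 0.02 |
| 0.20, 1.5 | 3 | 0.30 × 3/8 = 0.11 | 0.30 × 3/14 = 0.06 |
| 0.10, 1.0 | 3 | 0.10 × 3/8 = 0.04 | 0.10 × 3/14 = 0.02 |
| 0.30, 2.0 | 3 | 0.60 × 3/8 = 0.23 | 0.60 × 3/14 = 0.13 |

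**Scale.** If the 15.3 SDs applied to this average change, the 95% half-width for a mean of 50 would be 2.01 × SD/7.07: 0.142 mg/dL at SD 0.50 and 0.284 at SD 1.00. The central shift of 0.11 lies below both; the extreme of 0.23 lies between them. With d = 1.5, k = 3 and m = 8, the shift reaches the half-width when 50 × 0.142/(1.5 × 0.375) = 12.6 subjects are dialysed on treatment, so 13, or 25.3, so 26, at the larger SD.

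**Between groups.** With the same d, k and m in both groups, the net shift is (r_terlipressin − r_control) × d × k/m. Its sign follows whichever group has more RRT in the window, and it is zero only when rate and effect are equal. The documents give neither rate.

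**Is exclusion enough?** This was simulated with 60 data sets: 50 subjects, 10 dialysed; true change +0.6 in those 10 and −0.5 in the rest; d = 1.5; last three values affected; between-subject SD 0.3, residual SD 0.2. The model had categorical day, enrollment SCr and a random intercept. Last-day mean change (mg/dL):

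| Handling | 8 days | 14 days |
|---|---|---|
| No dialysis effect (target) | −0.270 | −0.294 |
| Post-RRT values used | −0.570 | −0.594 |
| Post-RRT values excluded | −0.433 | −0.432 |
| Highest pre-RRT value carried forward | −0.299 | −0.286 |

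Exclusion leaves 0.433 − 0.270 = 0.16 and 0.432 − 0.294 = 0.14 of the 0.30 shift. Carry-forward comes within 0.03. The last day is used here only to compare handling rules; the plan names no last-day contrast.

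**The case against.** Much can fairly be said for the plan.

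- **It does not say that these values will be used.** True: it is silent. A reader might infer that the plan chooses to score dialysis as improvement; the text does not support that. The values enter only because nothing removes them.
- **The overlap is limited.** Exclusion criterion 14 bars current, recent or imminent RRT, a stopping rule acts on SCr, and 72 hours is a maximum. This stands, and is why the range starts at one affected value. None of these rules says how an overlapping value is analysed, and the RRT clause itself provides for overlap.
- **The primary model appears comparative.** 15.1 estimates an association with receipt of terlipressin, which needs controls, while 13.1 and 13.2 make the comparison secondary. A reader might infer bias in favour of terlipressin against controls. The documents do not support that; the direction is unknown.
- **A last-day figure would look larger.** The central case gives 0.20 × 1.5 = 0.30 mg/dL on the last day. The plan specifies a repeated-measures analysis over the window, so the all-day average is the fairer illustration.
- **A lowered value may still lie above the subject's starting value.** True for that subject, but the group mean still moves down.
- **Efficacy is called descriptive, and dialysis is reported separately.** Both true, so dialysis is not hidden. A separate count does not correct the SCr estimate, and a descriptive mean is distorted just as a tested one is.

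**Conclusion.** The omission is certain from the text; its consequence is not quantified by it. Taken literally, the 13.1 window lets up to about three dialysis-lowered daily values per affected subject into the primary model. Within the terlipressin group that shifts the change towards benefit. Under the assumed central inputs the shift is modest (0.04-0.11 mg/dL over 8 days, 0.02-0.06 over 14); the wider assumptions span 0.02-0.23. All of these rest on an assumed RRT rate and SCr fall, and no between-group figure can be given.

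The wording difference between 13.1 and 15.1, and the missing Day 1 and end of treatment for controls, are minor. A reader might infer that 15.1 deliberately sets a longer window and admits more dialysed values, since SCr is collected to Day 14 or discharge whatever the treatment status. The term is undefined, and every statement of the endpoint uses the 13.1 window, so loose phrasing is the likelier explanation. The point should be fixed before analysis, because the repair is specific and cheap.

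**What to change.** Analysis only, with the same rule in both groups; no treatment rule changes.

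1. **Rule.** State in 13.1 and 15.1 that SCr from the first RRT session onward is not used as observed renal function. Report the number of subjects with RRT in the window, by group.
2. **Companion analysis.** Exclusion alone treats RRT as ignorable missingness. Report beside it an analysis that counts RRT as non-improvement: from first RRT, carry forward the highest SCr between the enrollment value (10.2) and first RRT. The change from enrollment then cannot be an improvement.
3. **Window.** Bring 15.1 to the 13.1 window. For controls, anchor Day 1 and end of treatment to the charted HRS-AKI treatment course.
4. **Data.** Use the RRT record already in Table 1, and confirm that it holds the date of first RRT in both groups.

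Cost: wording in two sections, one further analysis and one date check. The apparent improvement may be smaller; a few daily values per dialysed subject are lost; the carried-forward value is a convention and may overstate SCr; and RRT dates for controls depend on how complete the charts are.

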Dosing for M&O, albumin, or other vasopressor will be reported as it was recorded on the subject's chart.

For Prospective Terlipressin Group:

Terlipressin will be supplied in single-use, sterile 6-mL vials containing 1 mg of lyophilized Terlipressin acetate (equivalent to 0.85 mg Terlipressin free base) with 10 mg mannitol as a bulking agent/stabilizer.

Initial Dosing:

Terlipressin will be administered intravenously as a bolus injection (the vial will be reconstituted with 5 mL of sterile 0.9% sodium chloride solution and given over 1 minute at a dose of 0.5 mg).

- Continued dosing will be by 2 mg infusion per day. For continuous infusion, the dose of terlipressin is to be dissolved in 0.9% sodium chloride solution and infused with a pump.

Dose Modifications:

- If on Day 3 the SCr is not 30% lower from the baseline value, increase infusion dose to 4 mg per day.
- If on Day 5 the SCr is not 50% lower from the baseline value, increase infusion dose to 6-8 mg per day, per PI discretion. Dosing can be increased by more than 1 mg increment at Day 5 or beyond, up to a maximum of 8 mg/day.
- If the subject has infusion stopped for \geq 4 hours, a 0.5 mg bolus should be given prior to restarting infusion.
- The drug should not be used in subjects with severe coronary artery disease or in the setting of circulatory overload, pulmonary edema, or bronchospasm as determined by the Investigator. If drug therapy has been initiated, Investigator can also decide not to increase the dose, based on the patient's status with regard to the above, based on individual subject condition.

Collaborative Research Study, Version 4: 06/29/21
To Treat HRS-AKI Patients with Continuous Terlipressin Infusion

- If dosing is interrupted due to an adverse event, terlipressin may be re-started, at the discretion of the investigator, at the same or lower dose as per protocol. Terlipressin will not be restarted if dosing was interrupted due to cardiac ischemia or mesenteric ischemia.

Treatment Discontinuation:

- Terlipressin may be continued until 24 hours after serum creatinine has reached the lowest value possible as determined by Principal Investigator, up to a maximum of 14 days.
- After a minimum of 72 hours post final dose escalation and tolerability, if the SCr is at or above enrollment value, terlipressin should be discontinued.

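### The SCr window closes at a treatment end that depends on SCr for terlipressin and is undefined for controls, so the group comparison can be biased in either direction

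*Combined protocol and SAP*

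**What the plan says.** **Endpoint.** Section 13.1 defines the primary variable as "Improvement of renal function (SCr) from Day 1 through end of treatment, repeated measure analysis" and names no control group. Section 5.1 says the same. Section 13.2 lists the controlled version as the first secondary variable: "repeated measure analysis as compared to the Retrospective Control Group".

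**End of treatment, terlipressin** (Synopsis, Treatment Discontinuation):
- "Terlipressin may be continued until 24 hours after serum creatinine has reached the lowest value possible as determined by Principal Investigator", to a maximum of 14 days (repeated in section 10.3).
- At least 72 hours after the final escalation, "if the SCr is at or above enrollment value, terlipressin should be discontinued".
- "Terlipressin must be discontinued when the subject is to undergo liver transplantation, TIPS, or any other vasopressor therapy".
- After RRT starts, terlipressin can continue for up to 72 hours.

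**End of treatment, controls.** Section 8.4 asks for at least 48 hours of albumin and of vasopressor. No end date is defined.

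**Analysis.** Section 15.1 will "estimate changes in serum creatinine (SCr) over the study period". Section 10.3 runs the active study period to Day 14 or discharge. Section 15.1 also contains a terlipressin coefficient, since covariates are "sequentially removed if they do not confound the association between receipt of terlipressin and improvement in Scr". The primary model is thus comparative although the primary variable in 13.1 is not.

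**Collection.** Table 1 footnote f requires daily SCr to Day 14 or discharge, whether or not treatment continues. Section 12.2 requires it at baseline and then daily only while treatment lasts or until discharge.

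**The concern.** When the outcome helps decide the date on which the outcome stops being used, the values left in the analysis are a selected set. If that happens in one group under written rules, and in the other under unrecorded chart practice, a difference can appear with no drug effect.

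The asymmetry is concrete. A terlipressin subject who needs another vasopressor leaves the window at that moment. Other vasopressors are themselves qualifying control therapy (section 6.1), so the same switch need not close a control subject's window.

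The single-arm result in 13.1 is affected too. If treatment stops about a day after the lowest SCr, a rise soon afterwards lies outside the endpoint. The retreatment provision shows that recurrence is anticipated.

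**Working it through.** **1. The plan's own yardstick.** Inputs from sections 15.2 and 15.3: 50 versus 150 subjects, two-sided alpha 0.05, power 80%.

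Detectable difference = SD × (1.960 + 0.842) × √(1/50 + 1/150) = SD × 2.802 × 0.1633 = 0.4575 × SD.

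| SD | 1.00 | 0.75 | 0.50 | 0.20 | 0.10 |
|---|---|---|---|---|---|
| Computed | 0.457 | 0.343 | 0.229 | 0.091 | 0.046 |
| Printed | 0.46 | 0.34 | 0.23 | 0.11 | 0.05 |

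Four columns agree. The SD 0.20 entry should round to 0.09, a separate slip that does not affect this point.

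**2. What the window does with no drug effect.** Both groups were simulated from the same SCr process, and terlipressin follow-up was cut by coded versions of the Synopsis rules. The following are assumptions, not figures from the plan:
- enrollment SCr about 3.0 mg/dL, slope SD 0.1 mg/dL/day, daily random-walk SD 0.1, measurement SD 0.1;
- escalation judged against enrollment SCr;
- rescue represented by SCr reaching 1.5 times enrollment;
- the permissive nadir provision coded as a stop.

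False difference, terlipressin minus control, mg/dL (negative favours terlipressin). Model columns have controls to Day 14 and are read at mid-window.

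| Common SCr course | Last value, controls to Day 14 | Last value, controls ending at random Day 2-14 | Random-intercept model | Random intercept and slope |
|---|---|---|---|---|
| Flat | -0.05 | 0.00 | -0.10 | 0.00 |
| Rising 0.10/day | -0.69 | -0.12 | -0.22 | -0.01 |
| Falling 0.10/day | +0.38 | -0.07 | -0.06 | -0.05 |
| Dip, then rebound | about -0.8 | -0.20 | -0.39 | -0.47 |

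False rejections at 50 versus 150, on the last value with controls to Day 14 (nominal 2.5% per side):
- flat: 6.4% favouring terlipressin;
- rising: 99% favouring terlipressin;
- dip and rebound: 100% favouring terlipressin;
- falling: 63% favouring control.

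**3. Why the sign moves.** The rules pull in opposite directions. In a separate flat-course run (random-walk SD 0.2), controls at Day 14 had a mean change of +0.06. The terlipressin mean last on-treatment change, and its difference from control, were:
- nadir rule alone: +0.21, so +0.21 - 0.06 = +0.15;
- failure rule alone: -0.13, so -0.13 - 0.06 = -0.19;
- rescue rule alone: -0.06, so -0.06 - 0.06 = -0.12;
- all three: 0.00, so 0.00 - 0.06 = -0.06.

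Stopping at the nadir takes responders out early. Stopping on failure or rescue takes out those who are worsening.

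**4. Common window.** With Day 1 to Day 14 in both groups, the false difference was within 0.02 mg/dL in all four courses. Rejection was 2.5-3.3% favouring terlipressin and 2.3-3.3% favouring control. Applying the same stop rules to both groups also brought it within 0.02.

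**5. The collection gap.** Table 1 counts follow-up from the last dose, with the first visit at Day 7 ± 2. A site following 12.2 rather than footnote f has no required SCr for 7 - 2 = 5 to 7 + 2 = 9 days after stopping.

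**The case against.** A reader might infer that the window necessarily makes terlipressin look better. The documents do not support that. The sign depends on the SCr course, the control window and the estimator, and a falling course with controls followed to Day 14 favoured control on the last value.

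Other points on the plan's side:
- **Last on-treatment value is not a planned estimator.** Section 15.1 specifies a mixed model, which can largely absorb stopping that depends on observed SCr. With random slopes the error was at most 0.05 in the three courses without rebound. This stands, but rebound still left -0.47, and 15.1 does not state the random effects.
- **The nadir provision is permissive.** It says treatment may continue, not that it must stop. This stands, although discretion exercised on SCr still makes the window depend on SCr.
- **Silence about controls is not evidence.** Chart treatment may also have ended on response or failure. This stands. It means the two windows cannot be shown to be comparable, not that control curves ran on.
- **Values after stopping may be used.** Section 15.1 read with 10.3 points to Day 14 or discharge, so one cannot state as fact that they are ignored. What remains is a conflict with 5.1, 13.1 and 13.2.
- **Later rebound is partly covered.** Post-treatment SCr visits exist, and Day 30 and Day 90 SCr are secondary endpoints. These do not show the first days after stopping.
- **A fixed window lets in dialysed SCr.** Correct, and the fix must deal with it. The current window already admits up to 72 hours of it.

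**Conclusion.** The concern holds for the comparison in 13.2 and 15.1. The SCr window depends on the outcome for terlipressin, has no defined end for controls, and is described inconsistently across sections. For 13.1 alone, the narrower conclusion is that a rebound soon after stopping cannot be seen.

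The bias can go either way: toward terlipressin where SCr would rise or rebound, toward control where it is falling. In the rising and rebound courses the last-value error (-0.69 and about -0.8) exceeded the plan's 0.46 mg/dL at SD 1.00. Under rebound, the random-slope model's error (-0.47) was about equal to it. With controls of random length, the last-value error was no larger than 0.20.

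These sizes rest on assumed SCr courses and coded stop rules. The near-zero result for a common window is idealised, because discharge, death and dialysis are not among the modelled inputs. Only direction and sensitivity should be read from the figures. The inconsistency between sections rests on the text alone.

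**What to change.** No change to treatment or stopping rules is proposed.

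1. In 5.1, 13.1, 13.2 and 15.1, define one SCr analysis window for both groups: Day 1 to Day 14 from the start of HRS therapy, ending earlier only for discharge, death or liver transplant, regardless of when treatment stops or switches.
2. Define control Day 1 as the start of qualifying HRS therapy, and abstract chart SCr over the same window.
3. Do not count SCr after the start of RRT as improvement. Apply one rule in both groups, for example excluding those values or assigning an unfavourable one, with a sensitivity analysis.
4. Keep the analysis through end of treatment as a supportive on-treatment analysis.
5. Reconcile 12.2 with footnote f so that daily SCr continues to Day 14 or discharge after treatment stops.
6. State the random-effects structure in 15.1, and whether the primary result is single-arm (13.1) or comparative (15.1).

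**Cost.** Some extra chart abstraction for controls; footnote f already requires the prospective values. The terlipressin SCr change may look less favourable once values after stopping are included. Truncation at discharge remains, and discharge may itself track recovery.
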